## **10.2 Data Management and Processing**

### **10.2.1 Study Documentation**

Study documentation includes but is not limited to source documents, case report forms, monitoring logs, appointment schedules, study team correspondence with sponsors or regulatory bodies/committees, and regulatory documents that can be found in the DCI-mandated “Regulatory Binder”, which includes but is not limited to signed protocol and amendments, approved and signed informed consent forms, FDA Form 1572, CAP and CLIA laboratory certifications, and clinical supplies receipts and distribution records.

Source documents are original records that contain source data, which is all information in original records of clinical findings, observations, or other activities in a clinical trial necessary for the reconstruction and evaluation of the trial. Source documents include but are not limited to hospital records, clinical and office charts, laboratory notes, memoranda, subjects’ diaries or evaluation checklists, pharmacy dispensing records, recorded data from automated instruments, copies or transcriptions certified after verification as being accurate copies, microfiches, photographic negatives, microfilm or magnetic media, x-rays, subject files, and records kept at the pharmacy, at the laboratories and at medico-technical departments involved in the clinical trial. When possible, the original record should be retained as the source document. However, a photocopy is acceptable provided that it is a clear, legible, and an exact duplication of the original document.

### **10.2.2 Case Report Forms (CRFs)**

The electronic CRF will be the primary data collection document for the study. The CRFs will be updated in a timely manner following acquisition of new source data. Only the key personnel delegated on the delegation of authority log are permitted to make entries, changes, or corrections in the CRF.

An audit trail will be maintained automatically by the electronic CRF management system. All users of this system will complete user training, as required or appropriate per regulations.

### **10.2.3 Data Management Procedures and Data Verification**

Users of the electronic CRF will have access based on their specific roles in the protocol.

Completeness of entered data will be checked automatically by the eCRF system, and users will be alerted to the presence of data inconsistencies. Additionally, the data manager and project manager will cross-reference the data to verify accuracy. Missing or implausible data will be highlighted for the PI requiring appropriate responses (i.e. confirmation of data, correction of data, completion or confirmation that data is not available, etc.).

The database will be reviewed and discussed prior to database closure, and will be closed only after resolution of all remaining queries. An audit trail will be kept of all subsequent changes to the data.

### 10.2.4 Study Closure

Following completion of the studies, the PI will be responsible for ensuring the following activities:

- Data clarification and/or resolution
- Accounting, reconciliation, and destruction/return of used and unused study drugs
- Review of site study records for completeness
- Shipment of all remaining laboratory samples to the designated laboratories

## 11 STATISTICAL METHODS AND DATA ANALYSIS

All statistical analysis will be performed under the direction of the statistician designated in key personnel. Any data analysis carried out independently by the investigator must be approved by the statistician before publication or presentation.

### 11.1 Sample Size Estimation

This study will use the optimal two-stage design of Simon to test a hypothesis about response rate in subjects with NEPC treated with avelumab. Response will be defined as a complete (CR) or partial response (PR). Assuming that the response rate among subjects treated is 5%, the trial is designed to have 88% power with a one-sided type I error rate=5% to reject the null hypothesis of response rate of 5% when the true response rate was 20%. In the first stage, 18 subjects will be enrolled and if one or fewer responses are observed the trial will be terminated. However, if two or more responses are observed, an additional 26 subjects will be enrolled at the second stage for a total of 44 subjects. If five or more subjects respond, this new agent would be declared to have promising activity. This design has 88% power to conclude an agent is promising if its true objective response proportion is 20%; Type 1 error rate (one-sided) is 0.05 (this is the probability to conclude that a given agent is promising if its true objective response proportion is 5%). The probability of early termination under the null hypothesis is 0.77. These operating characteristics were selected to represent a reasonable compromise between high power, low false positive rates, and desire for small sample sizes, especially in the first stage. Allowing for 10% unevaluable rate, the target sample size is 49 subjects.

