# 1 PROTOCOL SYNOPSIS

Study Title: PD-L1 Inhibition as Checkpoint Immunotherapy for NeuroEndocrine Phenotype Prostate Cancer (PICK NEPC)					
Protocol Number	Pro00080869	Phase	II	Type	Interventional
Condition/Disease: Neuroendocrine prostate cancer (NEPC)					
Number of Subjects	18 in stage 1, 49 overall	Duration of Subject Participation		3 years	
Number of Study Centers	3-4	Duration of Study 8 years		Anticipated 12-18 months accrual time per stage, up to 3 years follow up	

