The target sample size is 18 in stage 1, and overall 49 evaluable subjects. For stage 1, Duke will serve as the single site for this study. For stage 2, the study would be expanded to include additional sites through the Department of Defense Prostate Cancer Clinical Trials Consortium (DOD PCCTC). All subjects will be followed for disease progression and death from the date that the subjects were enrolled to the protocol.

**Selection of Subjects:**Inclusion Criteria:

1. Neuroendocrine-like prostate cancer, based on histology OR based on clinical presentation as defined by meeting one of the two below criteria. All subjects must submit their primary tumor or metastatic biopsy pathology specimens to the Duke Cancer Institute where they will be centrally reviewed by Duke Pathology ([name]). Central Duke pathologic review is not required for screening but rather for confirmation of histologic subtype. Local pathologic review is sufficient for eligibility determination.
  - a. **Criterion 1:** Presence of 1 of 3 histologically proven diagnoses: **1)** Primary small cell carcinoma of the prostate, defined by classic histologic features such as small tumor cells with scanty cytoplasm, darkly stained nuclei with homogeneous chromatin pattern. The tumor cells do not form glandular structure but grow as solid sheets with frequent mitotic figures and necrosis; **2)** Intermediate atypical carcinoma of the prostate, which has histologic features distinct from small cell carcinoma or adenocarcinoma. The tumor grows as solid sheets or vague glandular structures. The tumor cells have moderate amounts of cytoplasm and centrally located, round and regular nuclei with fine, granular and homogeneous chromatin. Mitosis and necrosis are absent; **3)** mixed histology tumors of the prostate, containing both adenocarcinoma and neuroendocrine or small cell components.

- b. **Criterion 2:** Presence of histologically proven adenocarcinoma of the prostate without any sign of neuroendocrine or small cell histology that is radiographically progressing despite castrate levels of testosterone (<50 ng/mL) with the following poor risk features:
  - i. Prior progression despite therapy with either abiraterone acetate and/or enzalutamide

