**Data Analysis and Statistical Considerations:**

This study will use the optimal two-stage Simon design to test the hypothesis about modified PCWG3 using iRECIST radiologic response rate in subjects with NEPC treated with avelumab. Response will be defined as a complete (CR) or partial response (PR) using iRECIST criteria. Assuming that the response rate among subjects treated is 5%, the trial is designed to have 88% power with a one-sided type I error rate=5% to reject the null hypothesis of response rate of 5% when the true response rate was 20%. In the first stage, 18 subjects will be enrolled and if one or fewer responses are observed the trial will be terminated. However, if two or more responses are observed, an additional 26 subjects will be enrolled at the second stage for a total of 44 subjects. If five or more subjects respond, this new agent would be declared to have promising activity. This design has 88% power to conclude an agent is promising if its true objective response proportion is 20%; Type 1 error rate (one-sided) is 0.05 (this is the probability to conclude that a given agent is promising if its true objective response proportion is 5%). The probability of early termination under the null hypothesis is 0.77. These operating characteristics were selected to represent a reasonable compromise between high power, low false positive rates, and desire for small sample sizes, especially in the first stage. Allowing for 10% unevaluable rate, the target sample size is 49 subjects.

With 44 subjects, the objective response rate will be estimated with a standard error no greater than 10.7 percentage points. The Kaplan-Meier method will be used to estimate progression-free survival and overall survival distributions. Summary statistic will be computed for the duration of time on treatment distribution. The correlative science analyses will be considered exploratory and interpreted as such.

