## 5.10 Definition of Evaluable Subjects, On Study, and End of Study

Patients who consent but do not receive a dose of study drug will be replaced and will not be considered evaluable.

All subjects enrolled onto the study who receive at least one dose of avelumab will be included in the intention-to-treat analysis for the primary endpoint.

All subjects enrolled onto the study who receive at least one dose of avelumab will be evaluable for the secondary and exploratory endpoints.

Given the potential risk for delayed immune-related toxicities, safety follow-up must be performed 28 days after the last dose of avelumab administration.

The extended safety follow-up beyond 28 days after last study drug administration may be performed either via a site visit or via a telephone call with subsequent site visit requested in case any concerns noted during the telephone call.

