### **8.2.3 Enrollment**

Subjects will be enrolled only after all pre-treatment screening evaluations are completed and all eligibility criteria are met. Once the subject has been registered and found to meet all eligibility criteria, the subject will be approved for enrollment. Study treatment must not commence until the subject has received his/her identification number and enrollment approval from the lead site.

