### **11.9 Accrual and Follow-Up**

The target sample size is 18 subjects in stage 1, and 49 subjects overall if stage 1 is successful. Accrual is expected to be completed within 12-18 months after study activation for each stage. Stage 2 would require expansion to additional sites (2-3 additional sites) for accrual. All subjects will be followed for disease progression and mortality from the date that the subjects were enrolled to the protocol.

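### The 5-responder success rule holds its stated 5% error at 44 subjects, but the plan leads towards 49 analysed subjects and gives no cut-off for them

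*Combined protocol and SAP*

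**What the plan says.** Section 11.1, and the synopsis under Data Analysis and Statistical Considerations, set out the decision rule. There are 18 subjects in stage 1, with a stop at one response or none. Otherwise 26 more are enrolled, for 44 in all. Then: "If five or more subjects respond, this new agent would be declared to have promising activity". Power of 88%, one-sided error of 5% and early termination of 0.77 are stated for that design. The paragraph ends: "Allowing for 10% unevaluable rate, the target sample size is 49 subjects". The synopsis also ties estimation to the smaller number: "With 44 subjects, the objective response rate will be estimated".

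Elsewhere the overall number is 49:

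- Synopsis table: "18 in stage 1, 49 overall".
- Synopsis, Study Population: "The target sample size is 18 in stage 1, and overall 49 evaluable subjects".
- Section 11.9: "The target sample size is 18 subjects in stage 1, and 49 subjects overall if stage 1 is successful".

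The rules on who is counted are spread over several sections:

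- **5.10 and 8.8.3:** men who consent but are never dosed are not evaluable and are replaced. Dosed men who withdraw early are not replaced (8.8.3).
- **5.10:** all enrolled subjects "who receive at least one dose of avelumab will be included in the intention-to-treat analysis for the primary endpoint".
- **8.10.6:** men with no response assessment because of rapid progression or toxicity stay in the denominator as nonresponders.
- **8.11.4:** the main response analysis takes eligible subjects. Table 5 has a category for unknown or not assessable, and its note counts that category as treatment failure.
- **11.5.3:** ineligible subjects and those who cancel before any therapy are left out.
- **8.2.3:** "Subjects will be enrolled only after all pre-treatment screening evaluations are completed and all eligibility criteria are met".
- **11.2 (Analysis Sets):** defines no set and refers only to approximately 49 subjects.

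**The concern.** A cut-off of five responders gives a known false positive rate only for a known number of subjects. The plan derives it for 44 and aims to enrol 49. That is ordinary practice if about five of the 49 are expected to drop out of the analysis. Here almost nothing can make them drop out. Undosed men are replaced, so they use up none of the 49. Dosed men stay in, including those never assessed. The one clear way out for a dosed man is to be found ineligible after enrolment, and Section 5.10 would keep even him, while 8.11.4 and 11.5.3 would not.

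Two things are at stake. If more than 44 men are analysed under the five-responder rule, the stated 5% error generally no longer applies. And because the set is not fixed, whether the analysis uses 44, 47 or 49 men could be settled after responses are known, in an open-label trial where one responder can change the verdict.

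**Working it through.** **Inputs (Section 11.1).** Null rate 5%, target rate 20%, stage 1 size n1 = 18, continue on 2 or more responses, final total n = 44, success at r = 5 or more, unevaluable allowance 10%.

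**Formula.** For true response rate p,

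P(success) = Σ over k = 2 to n1 of P(X1 = k) × P(X2 ≥ r − k), with X1 ~ Bin(n1, p) and X2 ~ Bin(n − n1, p).

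**Step 1: reproduce the plan's figures at 44 (18 + 26).** Products were taken before rounding.

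| Stage 1 responses | P at p = 0.05 | P(reach 5 in 26 more) | Product |
|---|---|---|---|
| 2 | 0.1683 | 0.1386 | 0.02334 |
| 3 | 0.0473 | 0.3759 | 0.01776 |
| 4 | 0.0093 | 0.7365 | 0.00687 |
| 5 or more | 0.00155 | 1 | 0.00155 |

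The sum is 0.0495. At p = 0.20 the same four terms are 0.15778 + 0.22448 + 0.21468 + 0.28365 = 0.881. Early termination under the null is P(Bin(18, 0.05) ≤ 1) = 0.7735. All three agree with the plan. The inflation is also right: 44/0.9 = 48.9, rounded up to 49.

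**Step 2: same rule, 49 analysed (18 + 31).** At p = 0.05 the chances of reaching five from 2, 3 or 4 stage 1 responses become 0.2008, 0.4634 and 0.7961. The terms are 0.03380 + 0.02190 + 0.00742 + 0.00155 = 0.0647.

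**Step 3: every total from 44 to 49, stage 1 fixed at 18.**

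| Analysed | Error, 5 or more | Power, 5 or more | Error, 6 or more | Power, 6 or more |
|---|---|---|---|---|
| 44 | 4.95% | 88.1% | 1.78% | 84.1% |
| 45 | 5.25% | 88.4% | 1.94% | 84.9% |
| 46 | 5.55% | 88.6% | 2.10% | 85.6% |
| 47 | 5.85% | 88.9% | 2.27% | 86.2% |
| 48 | 6.16% | 89.1% | 2.45% | 86.7% |
| 49 | 6.47% | 89.2% | 2.64% | 87.2% |

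If one stage 1 man is excluded, so that stage 1 has 17, the error with five or more is 4.97% at 45, 5.25% at 46 and 5.81% at 48.

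**Step 4: allow for some exclusions.** The documents give no rate of late exclusion among dosed men, so this step is an assumption: each of 18 + 31 dosed men is excluded independently at a common rate, with both cut-offs kept.

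| Exclusion rate | Average error, both stages | Average error, stage 2 only |
|---|---|---|
| 2% | 6.0% | 6.3% |
| 5% | 5.4% | 6.0% |
| 10% | 4.5% | 5.5% |

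The average falls to 5% at a rate of 7.35% when both stages lose men, and at 15.7% when only stage 2 does.

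**Step 5: how often the verdict changes.** The five-responder verdict at 49 differs from that at 44 when the last five men supply the missing responder. That probability is the difference between the two success probabilities: 0.0647 − 0.0495 = 1.5% of trials at a true rate of 5%. It is 5.0% at a true rate of 10%, and 0.8923 − 0.8806 = 1.2% at 20%.

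**The case against.** The strongest reply is that Section 11.1, read alone, describes a 44-subject test. The sentence on five responders follows directly on the total of 44, the error and power belong to that design, and 49 appears only as an enrolment allowance. On that reading the word evaluable in the synopsis is a slip, and 49 elsewhere is an accrual figure. The arithmetic itself is sound, and if 10% of dosed men really were lost at random from both stages, average error would be 4.5%, below nominal.

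It can also be said that men might leave the analysis by other routes. Section 8.11.4 links one dose and one scan with a slash, which could mean both are needed. Section 7.1 lets men enrol on local pathology with central review to follow. And Section 11.5.3 already says that more studies are needed before medical decisions.

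Some of this stands. The 44-subject design is correct, the intended meaning may well be 44, and the effect is small. The rest does not remove the problem. No sentence limits the test to 44, and Section 5.10 places every dosed man in the primary analysis. The category in Table 5 for men who cannot be assessed, counted as failures, answers the slash. Section 7.1 calls local pathology sufficient for eligibility and does not say that central reclassification makes a man ineligible, so that route cannot be counted on to remove five men. The conflict over ineligible men would exist at any sample size, but here it also bears on which total the cut-off is applied to.

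**Conclusion.** The concern holds. The design and the inflation to 49 are each correct, but the success rule is not tied to the number of men the plan would analyse. Followed as written to 49 dosed men with no exclusions, the five-responder rule has a one-sided error of 6.47% against the stated 5%. That is the worst case and assumes stage 1 stays at 18. If 44 are analysed, the stated figures hold. Under independent exclusion from both stages, average error exceeds 5% unless about 7% or more of dosed men are removed.

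Power is not harmed and the 77% chance of stopping early under the null is unchanged. This should be fixed, but it does not undermine the design.

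**What to change.** 1. In the synopsis (Study Population), replace the description of 49 as evaluable with 44 evaluable and up to 49 enrolled.
2. Define one decision set and use it in 5.10, 8.11.4 and 11.5.3, saying whether a dosed man later found ineligible stays in. Keeping all dosed men, as 5.10 does, fixes membership at first dose. The analysis without ineligible men then becomes a sensitivity analysis.
3. In 11.1, state that the stage 1 and final rules apply to the first 18 and first 44 subjects of that set in order of first dose (error 0.0495, power 0.881). In 5.10, state that any further dosed subjects are reported descriptively and for safety but do not enter the rule.

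**Alternative to item 3, if everyone up to 49 is to be tested.** Stage 1 is still the first 18 of the set, and the final cut-off is pre-stated by attained total. Use five or more at any total up to 44 (error at most 0.0495; power 0.862 to 0.881 at 40 to 44, and 0.828 to 0.855 at 36 to 39). Use six or more at 45 to 49 (error 0.019 to 0.026, power 0.849 to 0.872). Restate error and power in 11.1 and 11.5.2.

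**Cost.** A text amendment with IRB approval and the CPC informed (12.2, 12.7), and no new data or procedures. Under the first-44 rule up to five dosed men fall outside the decision. If all dosed men form the set, the allowance is not needed and the target could simply be 44. Under the alternative, enrolment is unchanged, but power at 45 to 49 is 85% to 87% rather than the stated 88%, and the rule is conservative.

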### 11.2 Analysis Sets

This is a non-blinded single arm-arm phase II study of approximately 49 subjects, to assess the safety and efficacy of avelumab in patients with mCRPC

### 11.3 Patient Demographics and Other Baseline Characteristics

Eligible men will have metastatic CRPC with NEPC phenotype with measurable disease at baseline.

### 11.4 Treatments

Avelumab with ADT (unless pure SCPC present) will start on cycle 1 day 1 and continue every 2 weeks until progression or unacceptable toxicity.

## 11.5 Primary Objective

To estimate the overall response rate of men with NEPC treated with avelumab as determined by modified PCWG3 using iRECIST radiographic response.

### 11.5.1 Variable

Overall response rate (ORR) which is defined as either complete response (CR) or partial response (PR).

### 11.5.2 Statistical Hypothesis, Model, Method of Analysis

The null hypothesis is that the ORR is less than 5%. The trial is designed to have 88% power with a one-sided type I error rate=5% to reject the null hypothesis when the true response rate was 20%. The objective response rate will be estimated with a standard error no greater than 10.7 percentage points.

### 11.5.3 Handling of Missing values, censoring, and discontinuations

Ineligible subjects and subjects who cancel registration before receiving any therapy will not be included in the analyses. We will follow each patient long enough to avoid censoring due to end of study. The binomial test assumes that other censoring than due to end of study is rare. The study results are just important reference and more studies are necessary for medical decision making.

## 11.6 Secondary Objectives

1. To describe the efficacy of PD-L1 inhibition with avelumab as measured by PCWG3 using RECIST1.1
2. To describe the radiographic progression free survival (rPFS) of PD-L1 inhibition with avelumab using immune modified and PCWG3-modified RECIST 1.1 criteria in this setting.
3. To describe the overall survival of PD-L1 inhibition in this setting.
4. To described the toxicities and safety of PD-L1 inhibition with avelumab in men with metastatic neuroendocrine-like prostate cancer.

### 11.6.1 Key Secondary Objectives – analysis plan

The Kaplan-Meier method will be used to estimate both forms of progression-free survival as well as the overall survival distributions. Summary statistic will be computed for the duration of time on treatment distribution. The correlative science analyses will be considered exploratory and interpreted as such and reported using descriptive statistics and associations with clinical outcomes including response (radiographic) and progression free and overall survival.

### 11.6.2 Other Secondary Objectives – Analysis Plan

In addition, descriptive statistics will be calculated for secondary endpoints of safety profile and quality-of-life (QOL) endpoints, the continuous safety and QOL endpoints will be summarized as the

patient counts, mean, standard deviation, median, 25th and 75th percentiles, minimum and maximum. The categorical safety and QOL endpoints will be categorized using frequencies and percentages.

